Adjuvant phase: Three to eight weeks after salvage surgery, treatment will restart. If additional surgery is required after the initial salvage surgery (e.g., for completion, reconstruction), treatment will restart after the additional surgery. In Cycle 1-3: Nivolumab will be administered on Days 1 and 15 and lirilumab will be administered on Day 1 of each 28 day long cycle. In Cycle 4-6 and beyond: Nivolumab and lirilumab will be administered on Day 1 of each 28 day long cycle. Treatment with both study drugs will continue for a maximum of 6 cycles or until disease progression or recurrence, unacceptable toxicity or withdrawal of consent. Nivolumab 240 mg IV flat dosing will be administered through IV infusion, followed by lirilumab 240 mg IV flat dosing.

5.2.1 Cycle 1, Day 1

If screening assessments occur within a week before start of study treatment, then they may serve as the baseline cycle 1 day 1 visit and cycle 1 day 1 labs do not need to be performed. Laboratory evaluations do not need to be repeated to meet eligibility criteria on cycle 1 day 1, if they were done within 3 days of the first treatment dose.

5.3 Pharmaceutical Properties and Formulation for Lirilumab:

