- d) PET-CT or contrast-enhanced CT imaging of the chest, abdomen and pelvis will be obtained at baseline to rule out distant disease. Contrast-enhanced neck CT or MRI at the time of screening or registration and will be repeated 1-4 days prior to salvage surgery. Interval scans (contrast-enhanced neck CT or MRI) will be performed every 8 weeks following salvage surgery or as clinically indicated while on treatment. Follow-up imaging will be performed at the end of treatment (see footnote g).
- e) Archival tissue is acceptable. Some of this tissue will also be used for correlative study.
- f) Fresh biopsy is mandatory if tumor is accessible. Fresh tissue is also collected at the time of surgery. Biopsy will also be obtained at the time of progression or recurrence, if safe to perform.
- g) Participants, regardless if they receive the adjuvant therapy, will be followed for response (at the end of the window phase of the trial) until first disease progression or recurrence and for survival throughout the trial for a total of 5 years from time of salvage surgery (or from study registration if no salvage surgery was performed). Post-end of protocol treatment, if first disease progression or recurrence has not been confirmed, tumor assessments (contrast-enhanced neck CT or MRI and PET-CT) are to continue every 3 months (+/- 1 month) until first disease progression or recurrence, death, or 2 years post-date of salvage surgery (or from study registration if no salvage surgery was performed), then every 6 months until 5 years post-date of salvage surgery (or from study registration if no salvage surgery was performed). After first disease progression or recurrence has been confirmed, patients will be followed for survival by phone only, every 3 months (+/- 1 month) until death or 5 years post-date of salvage surgery (or from study registration if no salvage surgery was performed), whichever occurs first.
- h) Recommended in the setting of disease recurrence or progression only.
- i) Screening correlative blood collection may occur at screening or at pre-surgery. Pre-surgery correlative blood collection may occur any time from the day following neoadjuvant drug administration until surgery. EOT blood draw may occur after the EOT visit.

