11.1.4.3 Evaluation of New Lesions (for the window phase and adjuvant phase)

The finding of a new lesion should be unequivocal (i.e. not due to difference in scanning technique, imaging modality, or findings thought to represent something other than tumor (for example, some ‘new’ bone lesions may be simply healing or flare of pre-existing lesions). However, a lesion identified on a follow-up scan in an anatomical location that was not scanned at baseline is considered new and will indicate PD. If a new lesion is equivocal (because of small size etc.), follow-up evaluation will clarify if it truly represents new disease and if PD is confirmed, progression should be declared using the date of the initial scan on which the lesion was discovered.

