11.1.6 Disease-Free Survival and Overall Survival

Overall Survival: Overall Survival (OS) is defined as the time from salvage surgery (or from study registration if no salvage surgery was performed) to death due to any cause, or censored at date last known alive.

Disease-Free Survival: Disease-Free Survival (DFS) is defined as the time from salvage surgery (or from study registration if no salvage surgery was performed) to first progression or recurrence or invasive non-head-and-neck second primary or death from any cause, whichever occurs first. Participants alive without disease progression or recurrence are censored at date of last disease evaluation.

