13. STATISTICAL CONSIDERATIONS

This is a one arm phase II trial. The primary endpoint is 1-year disease-free survival (DFS) from point of salvage surgery. A 1-year DFS of 57% [36, 39-41] is the basis of the null hypothesis. Based on a 1-year DFS of 57%, the hazard is .5621 DFS events/person-year of follow up. A 30% reduction in that hazard would lead to a hazard of .3935. When 37 DFS events are observed among n=54 patients who receive salvage surgery and begin adjuvant treatment, this design has 81% power to detect a 30% reduction in the DFS hazard (using a one-sided 10% type I error rate, Wald's test). Assuming an exponential distribution, this corresponds to improving 1-year DFS from 57% to approximately 67.5% from using the adjuvant treatment.

Allowing for patients who may fail prior to salvage surgery, not receive the adjuvant portion of treatment, or for patients who are declared ineligible, n=58 patients will be registered to the trial.

The primary efficacy population includes all eligible patients who receive salvage surgery and begin adjuvant treatment. The Kaplan-Meier method will be used to estimate time-to-event endpoints.

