For secondary objectives: Best overall response (at the end of the window phase of the trial) will be summarized as a proportion with a corresponding exact 95% confidence interval (CI) (noting that a 'modified' version (no confirmation of initial CR or PR) of RECIST will be used for patients whose disease initially achieves a CR or PR: the patients' tumor will be resected prior to confirming the CR or PR at least 4 weeks after initial response). Adverse events will be classified and graded according to the CTCAE v.4.0. Frequencies of adverse events will be summarized. The distributions of n-year DFS and survival will be estimated using a Kaplan-Meier method with corresponding 95% confidence intervals for time-specific event time. Several correlative studies are also planned. Given the small sample size of this trial, these studies are exploratory. Samples will be collected at baseline and at post-baseline timepoints as outlined in the protocol. Markers from the samples (cluster differentiation markers from both tumor and circulating peripheral blood, see Section 9.1) will be summarized descriptively and graphically. Within subject changes in markers will also be analyzed. Assuming n=50 patients with useable baseline and post baseline markers, there is 81% power to detect .42 SD mean difference (Wilcoxon sign rank test two-sided 0.05 alpha level).

The following stopping rule will be used to monitor delays in salvage surgery due to excessive nivolumab and/or lirilumab-related toxicity: if 3 or more of the first 10 patients who begin protocol treatment experience treatment related toxicities which cause delays in definitive surgery, accrual to the trial will be suspended to further evaluate the events and decisions made regarding the overall status of the trial. If the true delay in surgery rate due to toxicity is 10% then the probability of suspending accrual is 7%; if the true rate is 20%, then the probability of suspending accrual is 32.2%; if the true delay in surgery rate due to toxicity is 30% then the probability of suspending accrual is 62%. Adverse events will be continuously monitored

throughout the trial by the study team with decisions made accordingly regarding the study status and patient entry throughout the duration of the trial.

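### Primary DFS is timed from surgery but analysed only in patients who start adjuvant treatment, so each failure excluded in the 3-to-8-week gap raises the 1-year estimate by about 1.1 points

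*Combined protocol and SAP*

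**What the plan says.** Three provisions matter together.

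- Population (Section 13): "The primary efficacy population includes all eligible patients who receive salvage surgery and begin adjuvant treatment".
- Clock (Section 11.1.6): "Disease-Free Survival (DFS) is defined as the time from salvage surgery (or from study registration if no salvage surgery was performed"). Sections 1.2 and 13 also time the primary 1-year endpoint from surgery.
- Gap (Section 5.2, adjuvant phase): "Three to eight weeks after salvage surgery, treatment will restart", or later if further surgery is needed. Sections 5.2 and 5.6 end protocol treatment at progression or recurrence.

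Section 13 expects some loss before adjuvant treatment. Its allowance for early failure is also for patients who may "not receive the adjuvant portion of treatment, or for patients who are declared ineligible, n=58 patients will be registered to the trial", against 54 analysed. The planned gain is described thus: "this corresponds to improving 1-year DFS from 57% to approximately 67.5% from using the adjuvant treatment". The only estimator named is Kaplan-Meier. For secondary objectives, Section 13 says: "The distributions of n-year DFS and survival will be estimated using a Kaplan-Meier method with corresponding 95% confidence intervals". It names no population for that estimate.

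On detection, footnote d of the Section 10 calendar says neck imaging "will be performed every 8 weeks following salvage surgery or as clinically indicated while on treatment". For an equivocal new lesion that is later confirmed, Section 11.1.4.3 says "progression should be declared using the date of the initial scan on which the lesion was discovered".

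Section 13 also has an event rule: if the accrual assumptions hold, more than 37 DFS events within four years means the primary endpoint is not met. The same paragraph warns that accrual may take longer.

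**The concern.** Entry to the analysis depends on something that happens after the clock starts. A patient who dies, or is found to have recurred, between surgery and adjuvant Cycle 1 Day 1 would not be expected to start adjuvant treatment and so leaves the primary population. Everyone who remains was event-free, as far as was known, throughout a gap that counts as follow-up. This is immortal time.

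The stated objective is DFS at one year from salvage surgery. What would be estimated is DFS from surgery among patients who got as far as adjuvant treatment. For resected patients as a whole, removing a gap failure can only raise the result. At stake are the headline 1-year figure and, under conditions set out below, its comparison with a fixed 57%.

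**Working it through.** **The plan's own figures reproduce.** The null hazard is -ln(0.57) = 0.5621 and 0.70 × 0.5621 = 0.3935; exp(-0.3935) = 67.5%. Power for a one-sample Wald test on the log hazard is Φ(√37 × |ln 0.70| - 1.2816) = Φ(0.888) = 81.3%, against 81% stated. The sample-size arithmetic is sound; the problem is the match of population to clock.

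**Bias per excluded failure.** If k gap failures are excluded beside 54 retained patients and the true 1-year DFS of all 54 + k is 57%, the apparent value is 0.57 × (54 + k)/54:

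- k = 1: 58.1%
- k = 2: 59.1%
- k = 3: 60.2%
- k = 4: 61.2%

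That is 1.1 to 4.2 points of the planned 10.5-point gain (67.5 - 57). The range 1-4 is borrowed from 58 - 54 = 4, a planning allowance for all losses. It neither caps nor estimates the number of gap failures.

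**How many failures the gap could hold.** Assume the null hazard applies in the gap and adjuvant start is uniform over 3-8 weeks. The share failing by week w is 1 - exp(-0.5621 × 7w/365.25): 3.2% at 3 weeks, 8.3% at 8 weeks, 5.7% (0.0574) averaged over the range. If a share d of these is detected and excluded, apparent DFS is 0.57/(1 - 0.0574d): 57.8%, 58.7% or 60.5% for d = 0.25, 0.5 or 1. Not all would be excluded: a recurrence first seen at the 8-week scan usually falls after adjuvant start and is counted. The documents do not give d.

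**Type I error.** Simulation used 60,000 null trials per case, 54 starters, a one-sided 10% Wald test, a look at four years and constant hazard. It assumes that the 57% counts all resected patients from surgery.

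| Setting | None excluded | Quarter | Half | All |
|---|---|---|---|---|
| Wald test, no event rule, 2-year accrual | 9.0% | 10.9% | 13.0% | 18.5% |
| With event rule, 2-year accrual | 2.4% | 2.8% | 3.1% | 4.2% |
| With event rule, 26.4 months | 3.8% | – | 5.1% | 6.8% |
| With event rule, 2.5 years | 6.4% | – | 8.9% | 12.1% |
| With event rule, 3 years | 8.8% | – | 12.7% | 18.2% |

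(58 patients at 2.2 per month take 26.4 months.)

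A gap hazard that differs from the average moves these figures even without exclusion. At 1.5 times the average, the Wald error is 12.1% with none excluded and 30.9% with all; at 0.5 times, 6.7% and 10.3%. Only the rise from the no-exclusion value belongs to this point.

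**The case against.** The strongest defence is that the plan is open about what it does. It states the restriction, allows for non-starters and frames the target as the benefit of adjuvant treatment. Follow-up continues for everyone (Section 5.7 and calendar footnote g), and secondary DFS is not expressly restricted. This shows that the data for a wider analysis will exist. It does not supply that analysis, and if the aim is the adjuvant effect, time at risk should begin with adjuvant treatment.

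The second defence is the event rule. A reader might infer from the 18.5% figure that the trial's false-positive rate exceeds its nominal 10%. The documents do not support that under the stated accrual: with the rule in force, error stays well below 10% at constant hazard. The caveat is that the rule depends on the accrual assumptions, which the plan itself says may fail.

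The third is that the 57% cannot be traced. Section 13 cites four series. Section 2.4 says that the studies it reviews took salvage-surgery patients with or without adjuvant therapy, but neither section says how the 57% treated early failures. This objection stands for the comparison with the null, though not for the estimate itself.

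The last is scale. The binomial standard error of 57% with 54 patients is √(0.57 × 0.43/54) = 6.7 points, so one or two exclusions shift the result by 0.2-0.3 standard errors. That is true, but the shift goes one way and is avoidable.

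**Conclusion.** The point holds and should be fixed. As an estimate of 1-year DFS from surgery in resected patients, the planned Kaplan-Meier figure is too high whenever a gap failure is excluded, by about 1.1 points each near 57%. That needs no assumption about the gap hazard, and the event rule does not remove it. The total is unknown because the documents give neither the number of gap failures nor the share detected before adjuvant start. At constant hazard it runs from 0.8 points (a quarter excluded) to 3.5 (all excluded).

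Two stronger readings go too far. A reader might infer that the test against 57% is certainly biased; that requires the 57% to count all resected patients from surgery, which the documents do not show. A reader might also infer that every gap failure is lost; the 8-week scan schedule means that some will be retained and counted.

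**What to change.** Preferred: make all eligible resected patients the primary population, with DFS from surgery whether or not adjuvant treatment starts, and restate n and the 37- and 38-event counts in Section 13. At the least, name this as a sensitivity analysis reported beside the primary. It does not depend on the detected share. Simulated Wald error is 9% (7-12% for gap hazards of 0.5 to 1.5 times average). The cost is that it includes patients who never had adjuvant treatment. Power is about 79% if 55-57 patients are resected (an assumption), taking the null hazard until adjuvant start and 0.3935 after. With 57 resected, about 46 null events are expected (43.5 × 57/54), against about 43 among 54 patients.

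If adjuvant starters remain primary, count time at risk from adjuvant Cycle 1 Day 1 (delayed entry). Label the surgery-clock estimate as conditional on being event-free at 3 weeks, the earliest entry; its null is 0.57/exp(-0.5621 × 21/365.25) = 58.9%. This loses about 7% of person-time (81.8 to 76.2 person-years under the null). At constant hazard, error is 9% and power 82% if all gap failures are detected before start. If only half are, and the rest surface at the 8-week scan, it is conservative: error 6%, power 73%. Across gap hazards of 0.5 to 1.5 times average and both detection shares, error is 3-18%, less steady than the all-resected analysis.

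Either way, report how many resected patients did not start adjuvant treatment and why. No new data are needed, since non-starters are already followed.

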5.2 Treatment Regimen

Patients will be premedicated with diphenhydramine, famotidine, and acetaminophen before lirilumab doses unless otherwise directed by treating investigator. Each treatment cycle will be 28 days long. On the days when both nivolumab and lirilumab are administered, nivolumab will be administered first, followed by lirilumab, with a 30-minute minimum duration time between the administration of nivolumab and lirilumab. Nivolumab infusion must be promptly followed by a saline flush to clear the line of nivolumab before starting the lirilumab infusion. Participants should be carefully monitored for infusion reactions during nivolumab and lirilumab administration. If an acute infusion reaction is noted, participants should be managed according to the algorithm described in Appendix C or in Nivolumab IB.

Nivolumab infusion time should be 30 (+/-10) minutes. A volumetric pump with a 0.2 - 0.22 micron in-line filter through an IV transfer set will be used.

Lirilumab infusion time should be 60 (+/-15) minutes. A volumetric pump with a 0.2 micron in-line filter through an IV transfer set will be used.

Window phase: Seven to twenty-one days prior to salvage surgical resection, a single dose of each study drug will be administered. Nivolumab 240 mg IV flat dosing will be administered through IV infusion, followed by lirilumab 240 mg IV flat dosing.

Salvage surgical resection: Each participant should be a candidate for salvage surgical resection to be able to participate in this study. Surgery should be performed no later than 4 weeks after study enrollment. Patients remain eligible to continue on study regardless of post-salvage surgery excisional margin status. Following salvage surgery, re-irradiation or additional chemotherapy is not permitted during the study period.

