Assuming accrual of approximately 2.2 patients per month, 2 years of accrual and 2 years of follow up are needed for the operating characteristics for the primary endpoint. Analysis of primary endpoint is estimated to take place therefore approximately 4 years after the trial opens to accrual (approximately 2 years of accrual and 2 years follow up) or when 38 DFS events have been observed. Due to possible delays in initiation of approval at other sites, in initiation of accrual itself, the accrual period could take longer and due to possible delays in data submission and processing, the actual analysis time for the primary endpoint could be later. Analysis of secondary endpoints will require more follow-up. Assuming that the stated accrual assumptions hold, if at any time within 4 years >37 DFS events are observed, the study will not have met its primary endpoint.

See also Data Sharing Agreement in section 12.

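### Section 13 gives two conflicting success rules: the Wald test at 37 events has the stated 81% power, but the failure limit of more than 37 events in 4 years has about 55% on the plan's timeline

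*Combined protocol and SAP*

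**What the plan says.** All of this is in Section 13 (Statistical Considerations) of the combined protocol and SAP.

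- **Null and alternative.** "A 1-year DFS of 57% [36, 39-41] is the basis of the null hypothesis", and "the hazard is .5621 DFS events/person-year of follow up". A 30% reduction gives 0.3935, or a 1-year DFS of about 67.5% under an exponential distribution.
- **Primary test.** "When 37 DFS events are observed among n=54 patients who receive salvage surgery and begin adjuvant treatment, this design has 81% power", using a Wald test at one-sided 10%.
- **Timing.** Accrual is about 2.2 patients a month for about 2 years, followed by 2 years of follow-up. The analysis is placed about 4 years after opening "or when 38 DFS events have been observed".
- **Count rule.** "Assuming that the stated accrual assumptions hold", the section adds, "if at any time within 4 years >37 DFS events are observed, the study will not have met its primary endpoint".

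No type I error or power is given for the count rule, and nothing says how it relates to the Wald test.

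**The concern.** In the power statement, 37 is an information target: the test needs that many events to reach its power. In the timing paragraph the same number becomes a ceiling, and exceeding it is failure. The two rules measure different things. The Wald test weighs events against person-years at risk, whereas the count rule looks only at the number of events by a calendar date. They can therefore give opposite verdicts on the same data.

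The analysis trigger makes this worse. The 38th event is the first count above 37. If it occurs within 4 years under the stated accrual, the trial has already been declared a failure at the moment its primary analysis falls due.

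The trial has one arm, so its conclusion rests on this section alone. With two prespecified rules and no order between them, the choice could be made after the results are known.

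**Working it through.** **Inputs.** From Section 13: 1-year DFS 57% under the null, hazard ratio 0.70, 37 events, n = 54 in the efficacy population, 58 registered, 2.2 patients a month, 2 + 2 years, one-sided 10%, exponential DFS. From Section 5.2: "Surgery should be performed no later than 4 weeks after study enrollment" and "Three to eight weeks after salvage surgery, treatment will restart".

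**1. The plan's own figure.** Null hazard = −ln(0.57) = 0.5621; alternative = 0.70 × 0.5621 = 0.3935. For a Wald test on the log hazard with d events, power = Φ(√d × |ln 0.70| − 1.2816). With d = 37: Φ(6.083 × 0.3567 − 1.2816) = Φ(0.888) = 81.3%. The stated 81% is reproduced, and it belongs to the Wald test.

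**2. The count rule on the stated timeline.** With uniform entry over 2 years and a cutoff at 4 years, a patient with hazard h has an event by the cutoff with probability p = 1 − (e^(−2h) − e^(−4h)) / (2h).

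- Alternative: p = 0.6849, so 54 × 0.6849 = 36.98 expected events.
- Null: p = 0.8049, so 54 × 0.8049 = 43.46 expected events.

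The limit of 37 therefore sits at the count expected when the regimen works as hypothesised. The event count D is Binomial(54, p), and the rule passes when D ≤ 37:

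- power = P(D ≤ 37 | p = 0.6849) = 55.3%
- type I error = P(D ≤ 37 | p = 0.8049) = 2.5%

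**3. Other timings, n = 54, no dropout.** Accrual of 26.4 months is 58 / 2.2. The lag is from enrolment to surgery. Event-free weeks are the time between surgery and adjuvant start, during which members of the efficacy population are assumed to have had no event. The lags and event-free weeks are assumptions guided by Section 5.2.

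| Accrual | Lag | Event-free weeks | p null / alternative | Type I error | Power |
|---|---|---|---|---|---|
| 24 months | none | 0 | 0.8049 / 0.6849 | 2.5% | 55.3% |
| 24 months | 2 weeks | 0 | 0.8006 / 0.6801 | 3.0% | 58.3% |
| 26.4 months | none | 0 | 0.7916 / 0.6707 | 4.4% | 63.9% |
| 26.4 months | 4 weeks | 0 | 0.7824 / 0.6606 | 6.3% | 69.6% |
| 26.4 months | 4 weeks | 5 | 0.7704 / 0.6476 | 9.5% | 76.2% |
| 26.4 months | 4 weeks | 8 | 0.7628 / 0.6395 | 12.0% | 79.9% |

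No row reaches 81%, and the closest one exceeds the 10% type I error.

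**4. How often the rules disagree.** These figures come from 200,000 simulated trials per case under the alternative, with the Wald test on the log hazard.

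- 24-month accrual, Wald test at 4 years: it rejects in 82.6% of trials, and 27.3% of all trials reject but have more than 37 events.
- 26.4 months with a 4-week lag: 81.4% and 13.3%.
- 24-month accrual, 38th-event trigger: the 38th event falls within 4 years in 44.7% of trials. The Wald test is significant at that moment in 25.0% of all trials (25.0 / 44.7 = 56% of those), yet the count rule has already declared failure.

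**5. One example.** Person-years expected by 4 years under the alternative are 36.98 / 0.3935 = 94.0. Take 38 events in 94 person-years. The hazard is 38 / 94 = 0.404, and ln(0.404 / 0.5621) × √38 = −0.330 × 6.164 = −2.03, well beyond −1.28. The Wald test succeeds and the count rule fails. At 38 events the Wald test needs only 38 / (0.5621 × e^(−1.2816/√38)) = 83 person-years.

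**The case against.** **The 55% is the low end of the range.** At 2.2 a month, 24 months yields 2.2 × 24 = 52.8 registrations, so 54 treated patients do not quite fit into 24 months, and registering 58 takes 26.4 months. DFS starts at surgery, which is later than enrolment. On that reading power is about 64% to 70%, and the overturned share falls to 13%. This stands as a caution on size. But the section itself states about 2 years of accrual plus 2 of follow-up, and those figures with n = 54 give an expected count of 37 almost exactly.

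**Some settings exceed 81%.** With 26.4 months and a 4-week lag, 52 evaluable patients give 82.2%, and an assumed 5% yearly loss to follow-up with 54 patients gives 86.2%. With 24-month accrual, 50 evaluable patients give 83.9%, and about 49 (52.8 × 54/58) give 88.9%. Accrual beyond about 31.5 months also exceeds 81%. These cases change the evaluable number, add a dropout rate the plan does not state, or break the accrual condition attached to the rule. The type I error is 14.4% with 52 patients and 23.6% with 49. They show that the count rule's properties depend heavily on timing and numbers.

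**The sentence may be only a monitoring benchmark.** It closes a paragraph on accrual and timing. Its wording, however, is a verdict on the primary endpoint, and nothing labels it as non-binding.

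**The form of the Wald statistic is assumed.** Section 13 does not name the scale. The log-hazard form reproduces the stated power, and an exact test gives 81.6%, so the conclusion does not turn on that choice.

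**Conclusion.** The conflict is real and affects the primary conclusion. The stated 81% power at one-sided 10% describes the Wald test. The count rule has about 55% power and 2.5% type I error on the 2 + 2-year timeline, and 58% to 80% power under the later-entry timings checked. About 27% of trials of an effective regimen would be overturned on the stated timeline, 25% if the Wald test is done at the 38th event, and 13% with 26.4-month accrual and a 4-week lag. These figures assume exponential DFS, uniform accrual, 54 evaluable patients and no dropout. The contradiction in the text does not depend on them: a trial analysed because its 38th event arrived within 4 years under the stated accrual cannot meet its endpoint, whatever the Wald test shows. The point must be fixed before analysis.

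**What to change.** In Section 13:

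1. Delete the sentence that declares failure when more than 37 DFS events occur within 4 years.
2. State that the primary conclusion rests only on the one-sided 10% Wald test of the DFS hazard, using events and person-time, in the primary efficacy population.
3. Replace the trigger of about 4 years or 38 events with one trigger that uses the event number in the power statement: the 37th DFS event, with 4 years given as its expected calendar time.

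If the sponsor prefers to keep a count limit, the section should either label it non-binding or make it the decision rule with its own type I error and power.

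The cost is a wording change, with no extra patients or procedures. In simulation with 24-month accrual, a Wald test at the 37th event rejects in 79.2% of trials under the alternative and 8.3% under the null, close to the stated 81% and 10%. The downside is that the analysis date follows the event rate. With 24-month accrual the 37th event falls at a median of 3.9 years under the alternative (5th to 95th percentile 3.2 to 4.8) and 3.1 years under the null (2.6 to 3.7). With 26.4-month accrual and a 4-week lag, the median under the alternative is 4.1 years (3.4 to 5.0).
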